5.7.4. Analyses of Other Efficacy Variables

The analyses of other efficacy variables will be the same as the primary analysis described in Section 5.7.1 and Section 5.7.2.

5.8. Analysis of Safety Data

The summary of safety and tolerability will be performed based on SAF.

The safety analysis will be based on the reported AEs, clinical laboratory evaluations, physical examination, vital signs and 12-lead ECG.

Thresholds for treatment-emergent Potentially Clinically Significant Values (PCSVs) in laboratory variables and vital signs are defined in [Appendix 10.4](#). Treatment-emergent PCSV is any PCSV developed or worsened in severity compared to the baseline during the treatment and follow-up period.

The time interval to detect any event or abnormality is between the first injection of study medication and EOS.

Subgroups are defined by key baseline factors recorded on the CRF and listed to be considered for safety analyses:

- Age group (≥ 6 to < 9 , ≥ 9 to < 12)
- Sex (Male, Female)
- Ethnicity: Hispanic or Latino (no/yes)
- Race (White, Black, Asian, Other)
- Duration of AD (< 5 years, ≥ 5 years)
- Baseline BMI (< 20 , ≥ 20)
- Baseline weight group (< 30 kg, ≥ 30 kg)

5.8.1. Adverse Events

Listings of TEAEs, serious TEAEs, and TEAEs resulting in death and study drug discontinuation will be generated.

Number and proportions of patients reporting TEAEs will be summarized for overall during the study, during the week 16 treatment period and during the follow-up period separately, sorted by decreasing frequency of SOC and PT based on the overall incidence for the combined dupilumab treatment groups.

Summaries of TEAEs will include:

- TEAEs
 - TEAEs by SOC/PT
 - TEAEs by SOC/HLT/PT
 - TEAEs by PT
 - Common TEAEs by SOC/HLT/PT (incidence with PT $\geq 5\%$)
 - Common TEAEs by SOC/HLT/PT (incidence with PT $\geq 2\%$)
 - TEAEs by severity by SOC/PT

- Severe TEAEs by SOC/PT
- TEAEs related to study medication as assessed by the investigator by SOC/PT
- Severe TEAEs related to study medication as assessed by the investigator by SOC/PT
- Serious TEAEs by SOC/PT
 - Serious TEAEs by SOC/PT
 - Serious TEAEs by SOC/HLT/PT
 - Serious TEAEs related to study medication as assessed by the investigator by SOC/PT
- TEAEs leading to permanent discontinuation of study treatment by SOC/PT
- Death by SOC/PT
- AESI by AESI category (see [Appendix 10.4](#)) and SOC/PT

The time to first AESIs (TEAE category), serious TEAE, or TEAE leading to permanent treatment discontinuation during the treatment period will be assessed by Kaplan-Meier estimates (K-M plot). In order to detect any safety signals, the hazard ratio (HR) will be provided together with the corresponding 95% confidence interval (CI) for the selected adverse events during the treatment period only. Hazard ratios will be calculated using a Cox model including treatment group and randomization strata as factors. The time is defined as the date of first specific event – the date of first dose + 1. Patients without a specific event will be censored at the end of treatment period.

5.8.2. Analysis of Clinical Laboratory Measurements

Laboratory measurements include clinical chemistry, hematology and urinalysis results, and will be converted to standard international units and US conventional units. Summaries of laboratory variables will include:

- Descriptive statistics of laboratory result and change from baseline by visit
- The number (n) and percentage (%) of patients with abnormal lab value during study whose screening and baseline values are normal (overall and per each lab parameter)
- The number (n) and percentage (%) of patients with treatment-emergent PCSVs overall during the study, during the treatment period and during the follow-up period
- Shift tables based on baseline normal/abnormal and other tabular and graphical methods may be used to present the results for parameters of interest

Listing of all laboratory parameters normal range, abnormal flag and treatment-emergent PCSV by patient and visit will be provided.

5.8.3. Analysis of Vital Signs

Summaries of vital sign variables will include:

- Descriptive statistics of vital sign variable and change from baseline by visit
- The number (n) and percentage (%) of patients with treatment-emergent PCSV
- Shift tables based on baseline normal/abnormal and other tabular and graphical methods may be used to present the results for parameters of interest

Listings of vital sign will be provided with flags indicating the treatment-emergent PCSVs.

5.8.4. Analysis of Physical Exams

The number (n) and percentage (%) of patients with abnormal physical exams will be summarized at baseline, end of treatment period and end of study by treatment group. A summary of treatment-emergent abnormal findings will be provided.

5.8.5. Analysis of 12-Lead ECG

Summaries of 12-lead ECG parameters by treatment group will include:

- Each ECG parameter and change from baseline
- The number (n) and percentage (%) of subjects with PCSV, depending on data
- ECG status (i.e. normal, abnormal) summarized by a shift table

Listings of ECG will be provided with flags indicating PCSVs.

5.9. Analysis of Pharmacokinetic Data

The following analyses will be conducted:

- Descriptive statistics of functional dupilumab concentrations in serum at each sampling time by dose
- Graphical presentations of median and mean (+/- SD) functional dupilumab concentration in serum vs nominal time profiles
- Graphical presentations of individual functional dupilumab concentration in serum vs actual sampling time profiles
- Assessment of the impact of anti-drug antibodies on functional dupilumab concentrations in serum.

No formal statistical analysis will be performed.

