The collective clinical data on the exposure versus efficacy and safety in the adults and pediatric population as observed to date supports a similar exposure-response relationship for efficacy and safety between the adult and pediatric populations down to 6 years of age and justify the approach of selecting dose regimens for this study based on the criteria of matching adult exposure.

To account for body size difference in the pediatric population and taking into account the observed large therapeutic indices of dupilumab, a tiered fixed dosing regimen was chosen over weight based (mg/kg) dosing for ongoing development. This approach reduces the risk of dosing errors that can occur with weight-based dosing, as well as allowing for dosing convenience by simplifying administration using a prefilled syringe/device.

A population PK model was used to describe the exposure of dupilumab in the population identified in this protocol. This model, initially based on drug concentration data from studies conducted in adults, was further informed by the exposure data of the study(s) conducted in pediatric patients (R668-AD-1412). The PK modeling for dupilumab has shown weight to be the most important covariate influencing exposure, with exposure being inversely correlated with body weight. Outside of the effect of body weight on PK, the existing data do not suggest an age-related effect on exposure.

Data gathered from NHANES (n=1269) show that median weight in the children aged 6 to 11 years old is = 32 kg (Q1=25, Q3=42). Simulations from the PK model suggest that the adult dose regimens (300 mg QW and 300 mg Q2W) may lead to systemic exposure in these children that is greater than the maximum exposure observed in adults. Hence, these doses are not supported by the safety data obtained in adults and will not be studied in children.

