In children with weight  $< 30$  kg, simulated mean weekly AUC at steady-state for the 300 mg Q4W regimen was similar to that in adults receiving 300 mg Q2W, while  $C_{max}$  was higher and  $C_{trough}$  was lower. Data gathered from this dose regimen will enable PK/PD modeling to better characterize the exposure-response relationship in pediatric patients. A less frequent dosing regimen is expected to enhance compliance, especially in a pediatric population.

The administration of the loading dose of dupilumab will allow systemic concentrations to reach effective concentrations faster, and potentially reduce the time to onset of clinical effect.

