NOTE: For patients who have vaccination with live, attenuated vaccines planned during the course of the study (based on national vaccination schedule/local guidelines), it will be determined, after consultation with a pediatrician, whether the administration of vaccine can be postponed until after the end of study, or preponed to before the start of the study, without compromising the health of the patient:

  - Patients for whom administration of live (attenuated) vaccine can be safely postponed would be eligible to enroll into the study.
  - Patients who have their vaccination preponed can enroll in the study only after a gap of 4 weeks following administration of the vaccine.
10. Planned or anticipated use of any prohibited medications and procedures during study treatment
11. Body weight <15 kg at baseline

12. Initiation of treatment of AD with prescription moisturizers or moisturizers containing additives such as ceramide, hyaluronic acid, urea, or filaggrin degradation products during the screening period (patients may continue using stable doses of such moisturizers if initiated before the screening visit)
13. Regular use (more than 2 visits per week) of a tanning booth/parlor within 8 weeks of the baseline visit
14. Active chronic or acute infection requiring treatment with systemic antibiotics, antivirals, antiprotozoals, or antifungals within 2 weeks before the baseline visit,  
NOTE: patients may be rescreened after infection resolves
15. Established diagnosis of a primary immunodeficiency disorder (eg, severe combined immunodeficiency, Wiskott Aldrich Syndrome, DiGeorge Syndrome, X-linked Agammaglobulinemia, common variable immunodeficiency), or secondary immunodeficiency. Patients suspected to have immunodeficiency based on their clinical presentation (history of invasive opportunistic infections eg, tuberculosis, other mycobacterial infections, histoplasmosis, listeriosis, coccidioidomycosis, pneumocystosis, chronic mucocutaneous candidiasis, etc or otherwise recurrent infections of abnormal frequency or prolonged duration suggesting an immune-compromised status, as judged by the investigator)
16. History of past or current tuberculosis or other mycobacterial infection  
Note: Irrespective of status of treatment or infection resolution. Tuberculosis testing will be performed on a country by country basis according to local guidelines if required by regulatory authorities or ethic committees.

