### 10.5.5. Analysis of Anti-Drug Antibody Data

The ADA variables described in Section 4.4 will be summarized using descriptive statistics by treatment group. Drug concentration data will be examined and the influence of ADAs on individual concentration-time profiles will be evaluated. Assessment of the potential impact of ADA on safety and efficacy may be provided.

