Arm A consists of patients receiving Q2W treatment, either 100 mg for patients weighing <30 kg or 200 mg for patients weighing ≥ 30 kg. Arm B consists of patients receiving Q4W treatment, 300 mg regardless of weight. Arm C consists of patients receiving placebo treatment Q2W and Q4W and matching the dupilumab Q2W and Q4W dose regimens.

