5. STATISTICAL METHODS

For continuous variables, descriptive statistics will include the following: the number of patients reflected in the calculation (n), mean, median, standard deviation, first quartile (Q1), third quartile (Q3), minimum, and maximum.

For categorical or ordinal data, frequencies and percentages will be displayed for each category.

All data will be summarized by 3 treatment groups (i.e. dupilumab q2w dose, dupilumab q4w dose and placebo).

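### The planned drug concentration summary pools 300 mg Q4W across both weight strata, so it cannot check the weight-specific trough predictions behind the dose choice

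*SAP*

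**What the plan says.** **Grouping for concentrations.** SAP 5.9 lists "Descriptive statistics of functional dupilumab concentrations in serum at each sampling time by dose", followed by mean and median concentration-time plots for which no grouping is named. SAP 5 gives the general rule: "All data will be summarized by 3 treatment groups (i.e. dupilumab q2w dose, dupilumab q4w dose and placebo". Protocol 10.5.4 asks for descriptive statistics at each time point and names no weight split.

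**Dose by weight.** SAP 2.1 states "Arm A consists of patients receiving Q2W treatment, either 100 mg for patients weighing <30 kg or 200 mg for patients weighing" at least 30 kg, and "Arm B consists of patients receiving Q4W treatment, 300 mg regardless of weight". The lower entry limit is exclusion criterion 11, "Body weight <15 kg at baseline". SAP Appendix 10.3 lists 30 kg for Germany.

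**Role of weight.** Protocol 3.2.2 says "The PK modeling for dupilumab has shown weight to be the most important covariate influencing exposure, with exposure being inversely correlated with body weight". Weight below 30 kg versus 30 kg or more is a randomisation stratum, and it is a listed subgroup for efficacy (SAP 5.7) and safety (SAP 5.8). No subgroup list exists for pharmacokinetics.

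**Predictions.** Protocol 3.2.2 treats the two weight groups of the Q4W arm separately. Below 30 kg, "simulated mean weekly AUC at steady-state for the 300 mg Q4W regimen was similar to that in adults receiving 300 mg Q2W", with Cmax higher and Ctrough lower. Above 30 kg, Cmax, Ctrough and weekly AUC are all predicted to be lower than on 200 mg Q2W.

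**The concern.** The doses were chosen to match adult exposure, and that reasoning was carried out within weight groups. The Q2W arm changes dose at 30 kg, so a by-dose table separates its weight strata automatically. The Q4W arm has one dose, so its strata are merged in exactly the summary where weight is expected to matter.

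Two things are lost. First, the trial would report no prespecified Q4W trough value for either weight group, although efficacy and safety are to be examined by weight group. Second, under the by-dose reading the natural comparison in children of 30 kg or more, 300 mg Q4W against 200 mg Q2W, is confounded with weight: one column contains only heavier children and the other contains both. Because exposure falls as weight rises, the lighter children would be expected to pull the Q4W column upward and hide some of the lower trough that the protocol predicts.

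**Working it through.** The plan states no figure on this point, so there is none to reproduce. The check is a reading of the grouping rules, followed by an illustration of size.

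**Step 1. Columns under each rule**

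| Arm and stratum | Dose | By dose (SAP 5.9) | Three groups (SAP 5) |
|---|---|---|---|
| Q2W, <30 kg | 100 mg | own column | Q2W |
| Q2W, ≥30 kg | 200 mg | own column | Q2W |
| Q4W, <30 kg | 300 mg | 300 mg Q4W | Q4W |
| Q4W, ≥30 kg | 300 mg | 300 mg Q4W | Q4W |

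Neither rule separates the last two rows. The SAP does not say which rule governs. SAP 5 itself uses the word dose for a regimen, so the three-group reading of SAP 5.9 is possible, and then 100 mg and 200 mg are pooled as well.

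**Step 2. Which predictions the samples can test**

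Protocol 4.3 treats every concentration as a trough, SAP 4.6 names only trough parameters, and footnote 9 to the schedule of events places PK sampling before dosing. A split therefore addresses Ctrough only:

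- At 30 kg or more, Q4W trough against 200 mg Q2W trough needs a Q4W ≥30 kg column.
- Below 30 kg, Q4W trough against adults on 300 mg Q2W needs a Q4W <30 kg value, and adult data from other studies.

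**Step 3. Spread in the single Q4W column, without a model**

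Dose per kg = 300 / weight: 300/15 = 20.0 mg/kg, 300/25 = 12.0, 300/30 = 10.0, 300/42 = 7.1. From the entry limit to the upper quartile of weight quoted in Protocol 3.2.2, this is a 42/15 = 2.8-fold range.

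**Step 4. Illustration of the between-stratum difference**

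Inputs: median 32 kg and quartiles 25 and 42 kg for ages 6 to 11 (Protocol 3.2.2, general population). Assumptions:

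- Weight is lognormal with log-SD = ln(42/25) / (2 × 0.6745) = 0.385, truncated to 15–90 kg. About 42% of children are then below 30 kg.
- Concentration is proportional to weight^-g. The documents give no g, so 0.5 to 1.5 is shown.

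Let R be the ratio of geometric means, <30 kg over ≥30 kg. The pooled geometric mean is then R^0.42 times the heavier stratum's and R^-0.58 times the lighter stratum's.

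| g | R | Pooled / lighter | Pooled / heavier |
|---|---|---|---|
| 0.5 | 1.33 | 0.85 | 1.13 |
| 0.75 | 1.54 | 0.78 | 1.20 |
| 1.0 | 1.78 | 0.72 | 1.27 |
| 1.5 | 2.37 | 0.61 | 1.44 |

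Worked line for g = 1.0: 1.78^0.42 = 1.27 and 1.78^-0.58 = 0.72.

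**Step 5. Cell sizes after a split**

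With 110 children in the Q4W arm, even strata give 110/2 = 55 each. At the 42% share above they would be about 46 and 64.

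**The case against.** The strongest reply is that little depends on this table. SAP 5.9 and Protocol 10.5.4 both say no formal statistical analysis of concentrations will be done. Pharmacokinetics is not a study objective and is not in the testing hierarchy. Q4W was randomised as one flat-dose arm, so reporting it as randomised is legitimate, and under the three-group rule both active arms are pooled over weight and remain comparable. Individual concentration profiles are planned, and the standard summaries include quartiles and extremes. A population model with weight as a covariate would be more informative than a cut at 30 kg, and Protocol 3.2.2 points to modelling for this purpose.

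Much of this stands and limits the weight of the point. It does not remove it. Protocol 10.5.4 makes the population analysis optional and reports it separately. Individual profiles and overall spread do not give a summary by stratum. The three-group reading avoids the unequal comparison only by pooling the Q2W strata too.

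Two stronger readings should be resisted:

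- A reader might infer that a split would verify all the exposure predictions. It would not: trough samples do not estimate AUC or Cmax, split or pooled.
- A reader might infer that the anti-drug antibody tables, which "will be summarized using descriptive statistics by treatment group" (Protocol 10.5.5), need the same split. The documents do not support that. The trend in Protocol 3.2.3 compares 2 mg/kg with 4 mg/kg cohorts within age groups and is not a weight effect. Some categories were sparse (six high-titer patients in that study), and the four active groups would leave out placebo.

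**Conclusion.** The point holds for the Q4W trough summary. On either grouping rule, SAP 5.9 merges two weight strata that the protocol randomises by and for which it predicts different exposure. The pooled summary cannot check the weight-specific Ctrough predictions. Under the by-dose rule, it also compares a heavier-only Q2W column with a mixed-weight Q4W column.

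The size is illustrative only: a between-stratum ratio of about 1.3 to 2.4, with the pooled geometric mean 15% to 39% below the lighter stratum and 13% to 44% above the heavier. This rests on an assumed exponent, on general-population weights rather than this trial's, and on applying to troughs a scaling that the documents state only for exposure in general. The 15 kg limit does not apply in Germany, so the actual weight mix may be heavier.

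The analysis is descriptive. A reader might infer that efficacy or safety conclusions are at risk, or that a dose is being questioned. Neither follows: no efficacy endpoint, power or alpha is touched, and the point concerns presentation of data, not dosing. The change is worth making before the SAP is final, but no trial conclusion depends on it.

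**What to change.** In SAP 5.9, replace the by-dose grouping for the descriptive concentration tables and the mean/median concentration-time plots with regimen by baseline weight stratum: 100 mg Q2W <30 kg; 200 mg Q2W ≥30 kg; 300 mg Q4W <30 kg; 300 mg Q4W ≥30 kg. State that this overrides the three-group default of SAP 5 for pharmacokinetics. Leave the antibody tables as planned.

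The cost is SAP wording and one more column than a by-dose table has, or two more than the three-group layout. The weight stratum is already recorded for randomisation, and no new data are needed. The price is precision: about 55 children per Q4W cell if the strata are even, which is an assumption, and fewer in one cell if they are not.

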5.10. Analysis of Immunogenicity Data

5.10.1. Analysis of ADA Data

The immunogenicity variables described in Section 4.7 will be summarized using descriptive statistics in the ADA analysis set. Frequency tables of the proportion of patients with pre-existing immunoreactivity, treatment-emergent, treatment-boosted, persistent ADA responses, and titer categories will be presented as absolute occurrence (n) and percent of patients (%) by treatment groups.

ADA response categories and titer categories are defined as follows:

- Pre-existing immunoreactivity, defined as either an ADA positive response in the assay at baseline with all post first dose ADA results negative, OR a positive response at baseline with all post first dose ADA responses less than 4-fold over baseline titer levels
- Treatment-emergent response, defined as a positive response in the ADA assay post first dose when baseline results are negative or missing. The treatment-emergent responses will be further characterized as Persistent, Indeterminate or Transient
 - Persistent Response - Treatment emergent ADA positive response with two or more consecutive ADA positive sampling time points separated by greater than 12-week period, with no ADA negative samples in between
 - Indeterminate Response - as a treatment-emergent response with only the last collected sample positive in the ADA assay
 - Transient Response - a treatment emergent ADA positive assay response that is not considered persistent or indeterminate.
- Treatment-boosted response, defined as a positive response in the ADA assay post first dose that is greater than or equal to 4-fold over baseline titer levels, when baseline results are positive
- Maximum Titer Values (Titer value category)
 - Low (titer <1,000)
 - Moderate ($1,000 \leq \text{titer} \leq 10,000$)
 - High (titer >10,000)

The following summaries will be provided based on AAS:

- Number (%) of ADA-negative patients
- Number (%) of patients with pre-existing immunoreactivity by treatment group and ADA titer categories
- Number (%) of treatment-emergent ADA-positive patients by treatment group and ADA titer categories
 - Number (%) of persistent treatment-emergent ADA-positive patients

- Number (%) of indeterminate treatment-emergent ADA-positive patients
- Number (%) of transient treatment-emergent ADA-positive patients
- Number (%) of treatment-boosted ADA-positive patients
- Listing of all ADA peak titer levels will be provided for treatment emergent and treatment boosted ADA response subjects and the neutralizing antibody status will be provided for subjects positive in the ADA assay.
- Scatter plot of ADA titers by ADA assessment time point indicated in Appendix 10.2
- Number (%) of patients in the three ADA titer categories by treatment group

5.10.2. Analysis of Neutralizing Antibodies (NAb)

Samples positive in the ADA assay will be further characterized for the presence of neutralizing antibodies (NAb) for dupilumab. The absolute occurrence (n) and percent of patients (%) with NAb status (positive or negative) will be provided for patients in the NAb analysis set.

5.11. Association of Immunogenicity with Exposure, Safety and Efficacy

5.11.1. Immunogenicity and Exposure

Association between ADA and systemic exposure to dupilumab will be explored by treatment groups. Plots of dupilumab concentration may be provided for analyzing the potential impact of treatment-emergent, persistent ADA response and titer (high, moderate or low) on PK.

